**After the preceding procedures and assessments are completed:**

- Study drug administration (record date and time of dose of study drug) ([Section 9](#))
- Vital sign measurements (sitting blood pressure, heart rate, respiratory rate, oral temperature) will be performed at 15, 30, and 45 minutes after the start of the infusion and at completion of the infusion ([Section 6.5](#))
- Pulse oximetry will be measured at 15, 30, and 45 minutes after the start of the infusion and at completion of the infusion ([Section 6.5](#))
- Concomitant medication assessment ([Section 6.10](#))
- AE assessment ([Section 6.9](#))

**After administration of study drug, the following post treatment procedures and assessments will be performed:**

- Vital sign measurements (sitting blood pressure, heart rate, respiratory rate, oral temperature): 30 minutes, 1 hour, and 2 hours following completion of the infusion; abnormal results to be repeated after 5 minutes of rest ([Section 6.5](#))
- Pulse oximetry: 30 minutes, 1 hour, and 2 hours following completion of the infusion ([Section 6.5](#))
- Day 28 ONLY: PK sample collection at 5 minutes, 1 and 2 hours after the completion of study drug infusion; record collection date and time for each PK sample ([Section 6.7](#))
- Day 28 ONLY: 12 Lead ECG (to be obtained in triplicate at 5 minutes after the completion of study drug infusion) ([Section 6.6](#))
- Concomitant medication assessment ([Section 6.10](#))
- AE assessment ([Section 6.9](#))

### **7.2.5 Final Maintenance Dose Visit (Cohort 2 Day 84)**

Subjects will return to the clinic for the final maintenance dose on Day 84 ±3 days. Subjects should be encouraged drink two 8-ounce glasses of water prior to dosing. The following procedures are to be performed prior to study drug infusion:

- Complete physical examination ([Section 6.3](#))
- Vital sign measurements (sitting blood pressure, heart rate, respiratory rate, oral temperature); to be measured immediately prior to the infusion ([Section 6.5](#))
- Pulse oximetry (to be measured immediately prior to the infusion) ([Section 6.5](#))
- Clinical safety laboratory tests (hematology, serum chemistry panel, urinalysis) ([Section 6.7](#))
- PK sample collection (collected just prior to the start of the study drug infusion) ([Section 6.7](#))
- Immunogenicity sample collection (collected just prior to the start of study drug infusion) ([Section 6.7](#))
- PD sample collection (collected just prior to the start of the study drug infusion) ([Section 6.7](#))
  - IgG, IgG subtypes (IgG1-4), IgA, IgM and CIC
  - Haptoglobin
- Concomitant medication assessment ([Section 6.10](#))
- AE assessment ([Section 6.9](#))

**After the preceding procedures and assessments are completed:**

- Study drug administration (record date and time of dose of study drug) ([Section 9](#))
- Vital sign measurements (sitting blood pressure, heart rate, respiratory rate, oral temperature) will be performed at 15, 30, and 45 minutes after the start of the infusion and at completion of the infusion ([Section 6.5](#))
- Pulse oximetry will be measured at 15, 30, and 45 minutes after the start of the infusion and at completion of the infusion ([Section 6.5](#))
- Concomitant medication assessment ([Section 6.10](#))
- AE assessment ([Section 6.9](#))

**After administration of study drug, the following post treatment procedures and assessments will be performed:**

- Vital sign measurements (sitting blood pressure, heart rate, respiratory rate, oral temperature): 30 minutes, 1 hour, and 2 hours following completion of the infusion; abnormal results to be repeated after 5 minutes of rest ([Section 6.5](#))
- Pulse oximetry: 30 minutes, 1 hour, and 2 hours following completion of the infusion ([Section 6.5](#))
- PK sample collection at 5 minutes, 1 and 2 hours after the completion of study drug infusion; record collection date and time for each PK sample ([Section 6.7](#))
- Concomitant medication assessment ([Section 6.10](#))
- AE assessment ([Section 6.9](#))

**7.2.6 Follow-up: Day 91, 112, and 140 ( $\pm 5$  days) (Day 91 is Early Termination [ET] Visit and Day 140 is End of Study [EOS] Visit)**

On Day 91, 112, and Day 140, subjects are to return to the clinic and the following procedures are to be performed.

*Note: If a subject prematurely discontinues study drug, the subject should be encouraged to attend, at a minimum, the early termination (ET) visit (Day 91), and subjects will also be encouraged to attend the remaining study visits (Days 112, and 140).*

*Subjects who prematurely discontinue from the study during follow up should attend the end of study (EOS) visit on Day 140.*

- Day 91 and 140 ONLY: Complete physical examination ([Section 6.3](#))
- Vital sign measurements (after 5 minutes of rest; sitting blood pressure, heart rate, respiratory rate, oral temperature): abnormal results to be repeated after 5 minutes of rest ([Section 6.5](#))
- Day 91 and 140 ONLY: Clinical safety laboratory tests (hematology, serum chemistry panel, urinalysis) ([Section 6.7](#))
- Day 91 and 140 ONLY: Pregnancy test ([Section 6.7](#))
- Day 91 and 140 ONLY: 12 Lead ECG ([Section 6.6](#))
- Day 91 and 140 ONLY: Serum tetanus antibody and VZV antibody See [Section 6.7.3](#) for additional information.
- Immunogenicity sample collection ([Section 6.7](#))
- PD sample collection ([Section 6.7](#))
  - IgG, IgG subtypes (IgG1-4), IgA, IgM and CIC
  - Haptoglobin
  - Day 91 and 140 ONLY: Direct Coombs test
  - Day 91 ONLY: D-dimer, antiphospholipid antibodies (lupus anticoagulant, anti-cardiolipin, and anti-beta-2-GP1 antibodies); antinuclear antibody titer; anti-double-stranded DNA antibody titer; complement component 3.
  - Day 91 and 140 ONLY: Cold agglutinins (titer and thermal amplitude)
  - Day 91 ONLY: Exploratory biomarkers (RNAseq)
  - Day 91 ONLY: Immune phenotyping by flow cytometry for measurement of CD3+CD4+ T, CD3+CD8+ T, monocytes, NK cells and B cells
  - Day 91 ONLY: Quantitative Coombs assay
- Concomitant medication assessment ([Section 6.10](#))
- AE assessment ([Section 6.9](#))

## **8. STUDY RULES**

### **8.1 Subject Withdrawal**

Every reasonable effort will be made to keep the subject in the study; however, if a subject withdraws from the study, the Investigator should complete and report the reasons for withdrawal as thoroughly as possible. The reason(s) for termination must be clearly documented on the appropriate page of the eCRF.

Subjects who have received at least one SYNT001 dose and withdraws or prematurely discontinue study drug should be encouraged to attend, at a minimum, the early termination (ET) visit (Day 112 for Cohort 1 or Day 91 for Cohort 2). Subjects in Cohort 2 will also be encouraged to attend the remaining follow up visits on Days 112, and 140.

If the subject fails to return for these assessments for unknown reasons, every effort (eg, telephone, email, and letter) should be made to contact them.

A subject's participation in the study may be prematurely discontinued for any of the following reasons:

1. The subject wishes to withdraw from the study.
2. Request by a regulatory agency or IRB.
3. Subject experiences a significant or intolerable AE.
4. The subject experiences a significant adverse change in vital signs, physical examination findings, or clinical laboratory parameter.
5. The subject has a need for a concomitant medication that is not permitted by the study protocol.
6. The subject experiences generalized impairment or mental incompetence that would result in the subject being unable to understand his or her participation in the study.
7. If, in the Investigator's medical judgment, further participation would be injurious to the health and well-being of the subject or is not in the best interest of the subject.
8. Administrative reasons, such as subject non-compliance or a major protocol violation.

### **8.2 Subject Replacement**

Enrolled subjects withdrawn for a reason other than an AE may be replaced.

### **8.3 Study Discontinuation**

The Sponsor has the right to terminate or to stop the study at any time. Reasons for study discontinuation may include, but are not limited to the following:

- The incidence or severity of AEs in this or other related studies indicates a potential health hazard to subjects
- Subject enrollment is unsatisfactory
- Drug supply issues

- Excessive subject self-withdrawal
- Significant protocol violations (eg, violation of eligibility criteria, dosing errors, missing data for study endpoint analysis)

## 8.4 Lost to Follow up

All reasonable effort should be made to contact any subject lost to follow-up during the study to complete assessments and retrieve any outstanding data. If the subject is unreachable after three good faith attempts, **at a minimum, the Investigator should follow up with a registered letter requesting contact** so safety data may be collected, recorded, and reported (if necessary).

## 8.5 Stopping Rule

### 8.5.1 Dose-Escalation Stopping Rule

Up to 8 subjects may be enrolled in Cohort 1. After 4 subjects reach Day 42, the Sponsor Medical Team will review available safety and PD data and will decide the dosing regimen for Cohort 2.

Dose-limiting toxicity (DLT) will be defined generally as severe (Grade 3) AEs occurring in  $\geq 2$  subjects that are determined to be clinically significant and considered related to study drug.

If 2 or more subjects at any time in any cohort have Grade 3 AEs that are determined to be clinically significant and considered to be related to study drug, dosing will be halted within that cohort and dose-escalation to a higher dose will not occur. If the dose-escalation stopping rule is met during Cohort 1 (10 mg/kg) all safety data and all available PD will be reviewed and the cohort may resume (if applicable) or a new cohort may be added at a dose at least 50% lower than the 10 mg/kg dose. If the stopping rule is not met in Cohort 1, dose-escalation may proceed up to a maximum of 30 mg/kg.

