
Subjects in Cohorts 1 and 2 will be enrolled at staggered intervals to facilitate adequate safety evaluation before dosing of subsequent subjects may proceed.
 
At 24-hour and 7-day intervals described below, available safety data (including, but not limited to, dose-limiting toxicities [DLTs], AEs, TEAEs, SAEs), and PD (including, but not limited to, total IgG levels) will be reviewed.
 
Safety Review of 24-hour Data for Cohorts 1 and 2, Subject 1
 
 
The first 2 subjects will be dosed at least 24 hours apart. A Dose Escalation Committee (DEC) 24-hour safety data review for the first subject in Cohort 1 will be performed to ensure that there are no overt safety concerns before dosing the second subject. The Sponsor Medical Team will conduct the 24-hour safety data review for the first subject in Cohort 2.
 
 
Safety Review of 7-day Data for Cohorts 1 and 2, Subjects 1 and 2
 
 
The 7-day safety data for the first 2 subjects in Cohort 1 will be performed by the DEC prior to dosing the remaining subjects in the cohort.
 
The 7-day safety data for the first 2 subjects in Cohort 2 will be performed by the Sponsor Medical Team prior to dosing the remaining subjects in the cohort.
 
 
The 24-hour and 7-day reviews will consider seriousness and severity of AEs/TEAEs/SAEs and relatedness to study drug, vital sign assessments, physical examinations, and clinical laboratory testing.
 
Safety (including but not limited to DLTs, AEs, TEAEs, and SAEs), and PD (including but not limited to IgG levels) data will be reviewed on an ongoing basis by the Sponsor Medical Team. In addition, at any point a review of all cumulative data may be performed.
 
 
If a DLT occurs, dosing will be halted within that cohort and dose escalation will not occur. NOTE: DLTs will be defined generally as severe (Grade 3) AEs occurring in <math>\geq 2</math> subjects that are determined to be clinically significant and considered related to study drug.
 
If any subject at any time during the study experiences a life-threatening AE (Grade 4) that is considered related to study drug, further dosing in all enrolled subjects will be suspended.
 
At any time during the study, the study or any ongoing study cohort may be discontinued if the Sponsor Medical Team determines that further drug exposure would pose an undue risk to subjects.
 
 
Dosing for any individual subject will be discontinued (ie, no further
				

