### 8.5.2 Study Stopping Rule

If any subject experiences a life-threatening AE (Grade 4) that is considered to be related to study drug, any further dosing in all enrolled subjects will be suspended until the Sponsor Medical Team has evaluated the event and determined the next appropriate course of action. At any time during the study, the study may be discontinued if the Sponsor Medical Team determines that further drug exposure would pose an undue risk to subjects.

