**Figure 2. Management of Moderate (Grade 2) Infusion Reactions**

**Figure 3. Management of Severe (Grade 3 or Higher) Infusion Reactions**

**Table 8. Grading and Management of Allergic or Infusion-Related Reactions**

Adverse Event	Grade				
	1	2	3	4	5
Infusion-related reaction	Mild transient reaction; infusion interruption not indicated; intervention not indicated	Therapy or infusion interruption indicated but responds promptly to symptomatic treatment (eg, antihistamines, non-steroidal anti-inflammatory drugs [NSAIDS], narcotics, IV fluids): prophylactic medications indicated for ≤24 hours	Prolonged (eg, not rapidly responsive to symptomatic medication and/or brief interruption of infusion); recurrence of symptoms following initial improvement, hospitalization indicated for clinical sequelae	Life-threatening consequences; urgent intervention required	Death
Allergic reaction	Transient flushing or rash, drug fever <38.0°C. Intervention not indicated	Therapy or infusion interruption indicated but responds promptly to symptomatic treatment (eg, antihistamines, NSAIDS, narcotics, IV fluids): prophylactic medications indicated for ≤24 hours	Prolonged (eg, not rapidly responsive to symptomatic medication and/or brief interruption of infusion); recurrence of symptoms following initial improvement, hospitalization indicated for clinical sequelae (eg, renal impairment, pulmonary infiltrates)	Life-threatening consequences; urgent intervention required	Death
Anaphylaxis	–	–	Symptomatic bronchospasm, with or without urticarial; parenteral intervention indicated; allergy-related edema/angioedema; hypotension	Life-threatening consequences; urgent intervention required	Death
Cytokine release syndrome	Mild reaction; infusion interruption not indicated; intervention not indicated	Therapy or infusion interruption indicated but responds promptly to symptomatic treatment (eg, antihistamines, NSAIDS, narcotics, IV fluids): prophylactic medications indicated for ≤24 hours	Prolonged (eg, not rapidly responsive to symptomatic medication and/or brief interruption of infusion); recurrence of symptoms following initial improvement, hospitalization indicated for clinical sequelae (eg, renal impairment, pulmonary infiltrates)	Life-threatening consequences; pressor or ventilator support indicated	Death

Abstracted from NCI CTCAE Version 4.03.

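### The only written bar on dose escalation names Grade 3 events; a related Grade 4 event suspends all dosing but is not tied to any bar on a higher dose

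*Protocol*

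**What the plan says.** **Bar on escalation (Protocol 8.5.1).** The halt sentence opens "If 2 or more subjects at any time in any cohort have Grade 3 AEs that are determined to be clinically significant", requires that the events be related to study drug, and gives the consequence: "dosing will be halted within that cohort and dose-escalation to a higher dose will not occur". If the rule is met in Cohort 1, the data are reviewed and the cohort may resume, or a new cohort may be added at a dose at least 50% lower. Otherwise, "If the stopping rule is not met in Cohort 1, dose-escalation may proceed up to a maximum of 30 mg/kg".

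**DLT definition (8.5.1 and synopsis, Study design).** Both places define a DLT as severe (Grade 3), clinically significant, related AEs in at least 2 subjects. Both qualify this with the word *generally*. The synopsis bar depends on that definition: "If a DLT occurs, dosing will be halted within that cohort and dose escalation will not occur".

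**Grade 4 (8.5.2 and synopsis).** The trigger is a single subject: "If any subject experiences a life-threatening AE (Grade 4) that is considered to be related to study drug". Dosing in all enrolled subjects is then "suspended until the Sponsor Medical Team has evaluated the event and determined the next appropriate course of action". The synopsis bullet says the same more briefly: if any subject "experiences a life-threatening AE (Grade 4) that is considered related to study drug, further dosing in all enrolled subjects will be suspended". Neither place mentions escalation.

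**Who decides.** After 4 Cohort 1 subjects reach Day 42, the Sponsor Medical Team reviews safety and PD data and sets the Cohort 2 regimen (4.2, 8.5.1, 13.6). Its required members are the Medical Monitor and the Sponsor Medical Lead. No statistical analysis supports the decision (11.8).

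**The concern.** A suspension and a bar on escalation are different protections. The suspension protects subjects now being dosed and ends when the Sponsor Medical Team chooses a course. The bar protects the next cohort, and 8.5.1 states no release from it.

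The 8.5.1 sentence is the only text fixed in advance that forbids a higher dose, and it names Grade 3 alone. Table 8 gives a concrete case, since anaphylaxis can be Grade 3 or Grade 4. Two related, clinically significant Grade 3 cases at 10 mg/kg would forbid a higher dose by rule. Two Grade 4 cases would leave the choice open. At stake is whether subjects in the next cohort may receive up to three times the dose (30 / 10 = 3) on judgement alone, in the situation where a rule set in advance is most wanted.

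**Working it through.** The plan states no operating characteristic for the rule, so there is no figure to reproduce. The check applies the two rules, as worded, to each pattern of related, clinically significant events in one cohort. Each subject is taken to have only the event shown.

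| Events in the cohort | Subjects with Grade 3 | 8.5.1 bar (needs at least 2) | 8.5.2 suspension (needs at least 1 Grade 4) | Higher dose forbidden by rule? |
|---|---|---|---|---|
| Grade 3 and Grade 3 | 2 | met | not triggered | yes |
| Grade 3 and Grade 4 | 1 | not met | triggered | no |
| Grade 4 and Grade 4 | 0 | not met | triggered | no |

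In the last two rows the suspension applies, and the Sponsor Medical Team decides both whether dosing resumes and whether the dose rises. With the bar unmet in Cohort 1, the 8.5.1 sentence permitting escalation up to 30 mg/kg applies.

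Three points limit the reach of the table.

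1. A subject with a Grade 4 event who also has a separate qualifying Grade 3 event counts towards the bar. The gap exists only where the Grade 4 event is that subject's sole qualifying event.
2. The word *generally* qualifies the DLT definitions, and so the synopsis bar. It does not appear in the 8.5.1 halt sentence.
3. The gap matters where a higher dose is still to be chosen, which is mainly the move from Cohort 1 to Cohort 2.

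No probability is attached to these patterns. The documents give no rates of related Grade 3 or Grade 4 events in this population. A simple binomial count would also treat every subject as fully exposed, although the first related Grade 4 event suspends all dosing.

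**The case against.** The strongest reply is that Grade 4 has its own, stricter tier. It takes one subject rather than two and stops the whole study rather than one cohort. On that reading, naming only Grade 3 in 8.5.1 is a deliberate division between the two sections. Elsewhere the documents do include higher grades explicitly: the Figure 3 title reads "Management of Severe (Grade 3 or Higher) Infusion Reactions", and 9.6.2 and SAP 4.7.1 use similar wording. But none of those places has a separate Grade 4 tier, so the contrast is only weak evidence about what 8.5.1 intends.

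Other safeguards also apply. A related life-threatening event is an SAE, so that subject's own dosing stops (8.5.3). Subjects do not move into later cohorts (5.1). The Sponsor Medical Team may discontinue the study for undue risk (8.5.2). The 8.5.1 halt itself ends in a review after which the cohort may resume. The earlier human experience in 2.2 is mild: no DLTs or SAEs after single doses up to 30 mg/kg in healthy volunteers, and in seven pemphigus subjects on the Cohort 1 regimen the only related AE seen in more than one subject was Grade 1 or 2 headache.

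All of this stands, and it makes the gap narrow. It does not close it. The stricter tier controls current dosing and is silent on escalation. Using *generally* to treat Grade 4 as a DLT is again sponsor judgement, and the 8.5.1 halt sentence lacks the word. The earlier samples are too small to rule the patterns out.

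**Conclusion.** The point holds as a gap in wording with a narrow practical effect. After two subjects with related, clinically significant Grade 3 events, a higher dose is forbidden. After one Grade 3 and one Grade 4, or two Grade 4, it is left to discretion. This rests on the literal text of 8.5.1 and 8.5.2 and on the affected subjects having no other qualifying Grade 3 event.

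A reader might infer more than the documents support:

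- *That Grade 4 toxicity is ignored.* It is not. One related event suspends all dosing.
- *That escalation would follow automatically.* It would not. The wording is permissive, and the Sponsor Medical Team would already have evaluated the Grade 4 event.
- *That the decision passes to the sponsor only in these patterns.* The team sets the Cohort 2 regimen in every case and may choose 10 mg/kg.
- *That a percentage can be put on the risk.* Any such figure would rest on invented rates.

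The absence of Grade 5 from 8.5.2 is minor. Section 10.3.1 treats death as the outcome of an AE, so a related fatal event is arguably already covered as life-threatening.

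**What to change.** Write 'Grade 3 or higher' in the DLT definition and in the halt sentence of 8.5.1, and make the same change in the synopsis DLT note. Keep the 8.5.2 suspension as it is. Optionally, name Grade 4 or 5 in 8.5.2 and in the matching synopsis bullet. The tiers then work together: one related Grade 4 event suspends all dosing, and two subjects at Grade 3 or higher halt the cohort and bar escalation.

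The cost is a few words in an amendment and a slightly higher chance that the cohort halt rule is met. A case that meets the new wording but not the present one has at least two subjects at Grade 3 or higher and fewer than two with a qualifying Grade 3 event. It must therefore include at least one related Grade 4 or 5 event. Where that event is Grade 4, 8.5.2 would already have suspended dosing.

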**Figure 1. Cohort Enrollment**

WAIHA = warm autoimmune hemolytic anemia

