**Table 4. Cohort Overview**

Cohort	No. of subjects	SYNT001 Dose	No. of Doses	Frequency of Doses
1	Up to 8	10 mg/kg	5	Weekly
2	Up to 12	Loading: 10, 20 or 30 mg/kg Maintenance: 10, 20 or 30 mg/kg	3 5	Weekly Every other week
2 Alternative weekly schedule	Up to 12	Loading: 10, 20 or 30 mg/kg Maintenance: 10, 20 or 30 mg/kg	3 10	Weekly Weekly

Up to 8 subjects may be enrolled in Cohort 1. After 4 subjects reach Day 42, the Sponsor Medical Team will review available safety and PD data and decide the dosing regimen for Cohort 2. The maintenance dose frequency may be increased to weekly (Cohort 2 alternative weekly maintenance schedule). Dosing regimen decisions for Cohort 2 will be communicated to the sites prior to Day 0 dosing.

The Sponsor Medical Team will consist of at least the Medical Monitor and the Sponsor Medical Lead. The Sponsor Medical Team may request that Investigators, other experts, or members within their organization participate in the review.

Subjects in Cohorts 1 and 2 will be enrolled at staggered intervals to facilitate adequate safety evaluation before dosing of subsequent subjects may proceed.

At 24-hour and 7-day intervals described below, available safety data (including, but not limited to, DLTs, AEs, TEAEs, SAEs), and PD (including, but not limited to, total IgG levels) will be reviewed.

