#### **Safety Review of 7-day Data for Cohorts 1 and 2, Subjects 1 and 2**

- The 7-day safety data for the first 2 subjects in Cohort 1 will be performed by the DEC prior to dosing the remaining subjects in the cohort.
- The 7-day safety data for the first 2 subjects in Cohort 2 will be performed by the Sponsor Medical Team prior to dosing the remaining subjects in the cohort.

The 24-hour and 7-day reviews will consider seriousness and severity of AEs/TEAEs/SAEs and relatedness to study drug, vital sign assessments, physical examinations, and clinical laboratory testing.

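### If Cohort 1 first meets the Grade 3 stopping rule after Cohort 2 has started above 10 mg/kg, no automatic pause covers the Cohort 2 subjects already on the higher dose

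*Protocol*

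**What the plan says.** The trigger in Protocol Section 8.5.1 is wide: "If 2 or more subjects at any time in any cohort have Grade 3 AEs" that are clinically significant and related to study drug. The consequence is narrow: "dosing will be halted within that cohort and dose-escalation to a higher dose will not occur". The synopsis agrees: "If a DLT occurs, dosing will be halted within that cohort and dose escalation will not occur". If Cohort 1 is the cohort that meets the rule, 8.5.1 requires a review of all safety data and available PD data. Cohort 1 may then resume, or a cohort at a dose at least 50% lower may be added. Cohort 2 is not mentioned. The section ends by allowing escalation up to 30 mg/kg if Cohort 1 has not met the rule.

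On timing, Section 4.2 says: "After 4 subjects reach Day 42, the Sponsor Medical Team will review available safety and PD data and decide the dosing regimen for Cohort 2". It adds: "Dosing regimen decisions for Cohort 2 will be communicated to the sites prior to Day 0 dosing". Cohort 1 may enroll up to 8 subjects. Its last infusion is on Day 28 and its last visit is on Day 112 (Table 2). Cohort 2 may receive 10, 20 or 30 mg/kg in each phase. Section 2.2 names 30 mg/kg loading with 10 mg/kg maintenance as the preferred starting regimen.

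Other controls exist. Entry of the first two Cohort 2 subjects is staggered, with a further check before the rest are dosed: "The 7-day safety data for the first 2 subjects in Cohort 2 will be performed by the Sponsor Medical Team". Section 13.6 has the Sponsor Medical Team review safety and PD data throughout. The synopsis gives the team a general power: "any ongoing study cohort may be discontinued if the Sponsor Medical Team determines that further drug exposure would pose an undue risk". Section 8.5.2 suspends dosing in all enrolled subjects, pending evaluation, after one related Grade 4 event.

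**The concern.** Two related Grade 3 cases at 10 mg/kg are the protocol's own signal that the dose should not rise. That signal can arrive after the dose has risen for some subjects. The rule then halts any 10 mg/kg dosing still under way in Cohort 1 and bars further escalation, but gives no instruction for subjects already at 20 or 30 mg/kg. Infusions falling due for them during the review go ahead unless someone decides otherwise.

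The signal would bear on those subjects. The human safety results summarized in Section 2.2 are single doses up to 30 mg/kg in healthy volunteers (five subjects at 30 mg/kg) and five weekly 10 mg/kg doses in seven pemphigus subjects. It reports no safety results from repeated human dosing above 10 mg/kg.

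**Working it through.** The plan gives no operating characteristics for the rule, so there is no figure to reproduce. The check is of scope and timing, followed by a count of infusions.

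**1. Who is stopped automatically?**

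| Provision | Trigger | Effect on a Cohort 2 subject already above 10 mg/kg when Cohort 1 triggers |
|---|---|---|
| 8.5.1 and synopsis | At least 2 subjects with related, clinically significant Grade 3 events | None stated; the halt is confined to the triggering cohort |
| 8.5.2 | One related Grade 4 event | Suspended, but Grade 3 events do not trigger it |
| 8.5.3 | The subject's own drug-related event | None |
| 24-hour and 7-day reviews (4.2) | Data from Cohort 2's own first subjects | None |
| Synopsis, 8.5.2 | Sponsor Medical Team judgement | Discretionary |
| 8.1, 8.3 | Investigator judgement, IRB or regulator request, Sponsor decision | Discretionary |

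**2. Can a late trigger occur?** The regimen decision needs 4 of up to 8 Cohort 1 subjects at Day 42. There are two routes to a later trigger:

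- Subjects 5 to 8 contribute the qualifying events.
- An earlier subject has a late event in follow-up. For the fourth subject, 112 − 42 = 70 days of observation remain at the decision point. With an assumed lag of 7 to 28 days to the first Cohort 2 dose, 63 to 42 of those days fall after it.

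These days are time in which a signal can arise, not dosing time: at Day 42 the subject is 42 − 28 = 14 days past the last infusion. If no Cohort 1 subject is still within Days 0 to 28, the halt in Cohort 1 withholds no infusion.

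**3. What falls due during the review?** Cohort 2 infusion days are 0, 7, 14, 28, 42, 56, 70 and 84 (8 infusions), or every 7 days from 0 to 84 (13 infusions). For a trigger just after the infusion on day t and a review of R days, count infusion days d with t < d ≤ t + R and multiply by the dose. R is not stated; 7, 14 and 28 days are assumed. Visit windows are ignored.

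| Phase and dose | R = 7 | R = 14 | R = 28 |
|---|---|---|---|
| Loading 30 mg/kg, t = 0 | 1 × 30 = 30 mg/kg | 2 × 30 = 60 | 2 × 30 = 60 (later infusions are maintenance) |
| Every-other-week maintenance 20 mg/kg, t = 28 | 0 | 1 × 20 = 20 | 2 × 20 = 40 |
| Every-other-week maintenance 30 mg/kg, t = 28 | 0 | 1 × 30 = 30 | 2 × 30 = 60 |
| Weekly maintenance 20 mg/kg, t = 28 | 1 × 20 = 20 | 2 × 20 = 40 | 4 × 20 = 80 |
| Weekly maintenance 30 mg/kg, t = 28 | 1 × 30 = 30 | 2 × 30 = 60 | 4 × 30 = 120 |
| Maintenance 10 mg/kg | none above 10 | none above 10 | none above 10 |

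Under the 30/10 regimen, only the three loading infusions exceed 10 mg/kg: 3 of 8, or 3 of 13 on the weekly schedule. A given subject is then affected only by a trigger between that subject's Day 0 and Day 14.

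**4. How likely is it?** The per-subject probability p of a qualifying event is not in the documents. As illustration only, assume 8 independent Cohort 1 subjects and take P(at least 2 of 8) − P(at least 2 of 4):

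| p (assumed) | At least 2 of 4 | At least 2 of 8 | Difference |
|---|---|---|---|
| 0.05 | 1.4% | 5.7% | 4.3% |
| 0.10 | 5.2% | 18.7% | 13.5% |
| 0.20 | 18.1% | 49.7% | 31.6% |
| 0.30 | 34.8% | 74.5% | 39.6% |

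Differences are taken before rounding. They cover the first route only. They overstate it if subjects 5 to 8 are well advanced when Cohort 2 starts, and they do not require a Cohort 2 subject to be above 10 mg/kg at that moment. The spread shows that the inputs do not fix a probability.

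**The case against.** The strongest reply is the closing sentence of 8.5.1. Escalation is permitted only if Cohort 1 has not met the rule, so permission for 20 or 30 mg/kg might be taken to lapse once it does. That is a sensible reading for new starts. It does not say what happens to subjects already escalated, and the sentence that does prescribe a halt confines it to one cohort.

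Second, the text sets when the Cohort 2 regimen is decided, not that Cohort 2 must start while Cohort 1 is open, and Figure 1 may show an ordering. This stands as a limit: overlap is permitted by the available text but cannot be checked against the figure.

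Third, the graded response is a deliberate choice, with Grade 3 halting a cohort and Grade 4 halting everyone, and single doses up to 30 mg/kg were well tolerated. That argues against treating Grade 3 like Grade 4. It does not argue against a short pause confined to doses above the one that produced the signal.

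A reader might also infer that only the Sponsor Medical Team could stop Cohort 2. The documents do not support that: Sections 8.1 and 8.3 give routes to the Investigator, IRB, regulator and Sponsor. Nor is oversight absent, since a Cohort 1 trigger requires a review. What is missing is an automatic pause while that review runs.

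**Conclusion.** The gap is real but limited. As written, a Cohort 1 trigger that comes after Cohort 2 has started above 10 mg/kg leaves those Cohort 2 subjects without a default pause. For a subject loading at 30 mg/kg, one or two further 30 mg/kg infusions are at stake in an assumed 7- or 14-day review. More are at stake only if the team chooses 20 or 30 mg/kg weekly maintenance and the review is long. If Cohort 2 receives 10 mg/kg throughout, no higher-dose infusion is at stake.

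Two stronger readings should be resisted. The 70 days from Day 42 to Day 112 are not a period in which 10 mg/kg is stopped while 30 mg/kg continues; that contrast needs Cohort 1 subjects still within Days 0 to 28. And no probability of a late trigger can be claimed.

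The conclusion assumes that Figure 1 imposes no sequential restriction. The change should be made, because the present default is the less cautious one and correcting it is cheap.

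**What to change.** Keep the existing sentence in Section 8.5.1 and the synopsis, so that the halt in the triggering cohort and the bar on escalation stay as they are, and add:

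> If the rule is met in one cohort while subjects in another are being dosed, any scheduled infusion in the other cohort at a mg/kg dose above that at which the rule was met will be withheld until the Sponsor Medical Team has reviewed all safety data and decided how to proceed. Infusions at or below that dose may continue at the team's discretion.

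Framing this by infusion rather than by cohort makes it workable for a 30/10 regimen: loading infusions would be withheld, and 10 mg/kg maintenance need not be. It uses the suspend-pending-evaluation form already in 8.5.2.

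The cost is one sentence in two places. If the rule is met, higher-dose infusions and IgG suppression may be interrupted for the length of the review. If it is never met, there is no cost. Should Figure 1 already require Cohort 1 to finish before Cohort 2 starts above 10 mg/kg, stating that in 8.5.1 would serve instead.
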